7.10.7. Cortisol Assessments

Cortisol assessment is performed at screening to obtain baseline values and at subsequent visits to assess for hypercortisolism while on treatment. The proportion of subjects with ≥ 15 nmol/L change from baseline of NSC (Night-time salivary cortisol) will be summarized by treatment and placebo group.

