8.2.5.3. Cortisol Assessments

Saliva samples for measurement of night-time salivary cortisol (NSC) will be obtained at timepoints designated in the SoA (Section 1.3) to screen for hypercortisolism (Pappachan, 2017). The cortisol screening assessment is performed at screening to obtain baseline values and at subsequent visits to assess for hypercortisolism while on treatment. The NSC samples must be collected between 8:00pm and 12:00am before submitting the sample for processing at the specified visit. If sample is not collected during this time, repeat sample must be collected.

The screening NSC assessment should be performed as early as possible during the screening period to allow sufficient time for samples to be resulted prior to randomization. Subjects should be provided with NSC collection kit at the first screening visit, when possible, to allow sample collection return at the following clinic visit. Subjects will not be deemed ineligible if screening NSC samples have been submitted but have not been resulted by Day 1 and may be randomized. Subjects with missing screening values will still have NSC assessments performed at the other scheduled visits as designated in the SOA.

If screening value is >15 nmol/L, Medical Monitor (or designee) may request further workup should the value be of clinical concern; however, values >15 nmol/L will not be exclusionary. The screening NSC is a safety assessment, and not an eligibility criterion.

For on-treatment values that are >15 nmol/L AND above the screening value, a repeat NSC should be performed (sample should be collected at approximately the same time as the screening sample). If the repeat assessment is still > 15 nmol/L AND above the screening value, an additional screening test for hypercortisolism will be done (either overnight dexamethasone (1 mg) suppression test [DST] or a 24 h collection for urinary free cortisol [UFC]) level.

If a screening value is not available, and on-treatment value is >15 nmol/L, a repeat NSC should be performed and if the repeat assessment is still >15 nmol/L, an additional test for hypercortisolism will be done (either a DST or a UFC).

The Medical Monitor (or designee) will provide guidance on the appropriate assessment based on the individual subject for subsequent test values that are also >15 nmol/L based on the subject profile.

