4.1.5. Safety Endpoints

- Frequency and severity of TEAEs and SAEs
- Number of subjects who discontinued due to TEAEs and due to related TEAEs
- Incidence and shifts of clinically significant physical examination findings, ECG data and laboratory abnormalities; safety laboratory evaluations include hematology, blood biochemistry and urinalysis, serum, salivary, and urinary cortisol as appropriate
- Change from baseline in
 - Insulin-like growth factor 1 (IGF-1)
 - Bone biomarkers: Carboxy-terminal collagen crosslinks (CTX), N-terminal propeptide of type 1 collagen (P1NP) and osteocalcin
 - Thyroid stimulating hormone (TSH)
- Absolute and % change from baseline in lumbar spine, total hip, and femoral neck bone mineral density (BMD) as assessed by dual X-ray absorptiometry (DXA)
- Incidence and characteristics of anti-drug antibodies (ADA) and neutralizing antibody (NAb) after dosing (e.g., titer and binding specificity, to the FGF21 and polyethylene glycol [PEG] part of pegozafermin)
- Impact of the presence of ADAs on serum pegozafermin concentrations and clinical safety

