5. DEFINITIONS

5.1. Baseline Definition

For efficacy, safety (except ALT, AST, lipids, and vital signs), and biomarkers each subject's baseline value for that measurement will be defined as the last non-missing value collected on or before the day of first study drug dose, or randomization date + 5 days if subjects have never been dosed. Other baseline values, such as demographics and pertinent medical history etc., is defined as last available value before randomization date.

The definition of baseline of lipid panel labs is the average of last non-missing screening fasting values and Study Day 1 value (Pre-dose, fasting).

The definition of baseline vital signs is the average of the last non-missing screening values and Study Day 1 value (Pre-dose). If there is Case Report Form (CRF) average value on duplicate measurements of BP and/or Pulse on Study Day 1, only the individual values will be included in the baseline derivation.

Baseline ALT and AST were defined as below:

Table 3: Baseline Definition for ALT and AST Values

ALT/AST Screening Assessments			Day 1 ALT/AST Assessment	Baseline Value
Assessment 1	Assessment 2	Assessment 3 (if applicable)		
Normal	Normal	Not applicable	Any	Average of Assessment 1, Assessment 2 and Day 1 (3 tests)
Normal	Abnormal and ≤40% increase from Assessment 1	Not applicable	Any	Average of Assessment 1, Assessment 2 and Day 1 (3 tests)
Normal	Abnormal and >40% increase from Assessment 1	Normal or ≤40% increase from Assessment 1	Any	Average of Assessment 1, Assessment 2, Assessment 3 and Day 1 (4 tests)
		Abnormal and >40% increase from Assessment 1	Not applicable, subject excluded	Not applicable, subject excluded
Abnormal	≤40% increase from Assessment 1	Not applicable	Any	Average of Assessment 1, Assessment 2 and Day 1 (3 tests)
Abnormal	>40% increase from Assessment 1	≤40% increase from Assessment 1	Any	Average of Assessment 1, Assessment 2, Assessment 3 and Day 1 (4 tests)
		>40% increase from Assessment 1	Not applicable, subject excluded	Not applicable, subject excluded

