* NSC samples must be collected between 8:00pm and 12:00am before submitting the sample for processing at the specified visit. If sample is not collected during this time, repeat sample must be collected. If screening value is >15 nmol/L, Medical Monitor (or designee) may request further workup should the value be of clinical concern; however, values > 15 nmol/L will not be exclusionary. The screening NSC is a safety assessment, and not an eligibility criteria. The screening assessment should be performed as early as possible during the screening period. Subjects should be provided with NSC collection kit at the first screening visit, when possible, to allow sample collection return at the following clinic visit.	Enhanced liver fibrosis (ELF) panel including concentrations of serum biomarkers: tissue inhibitor of matrix metalloproteinases-1 (TIMP-1), amino-terminal type 3 procollagen peptide (P3NP), and hyaluronic acid (HA) N-terminal type 3 propeptide of collagen (Pro-C3) Fasting free fatty acids (FFA) and Adipo-IR index (fasting FFA x fasting insulin) ^a FIB-4 index (derived calculation) Alpha feto-protein (AFP) (for F4 patients only) MELD Na ⁺ (for F4 patients only)

For on-treatment values that are >15.0 nmol/L AND above the screening value, a repeat NSC should be performed (sample should be collected at approximately the same time as the screening sample). If this repeat assessment is still > 15.0 nmol/L AND above the screening value, an additional screening test for hypercortisolism will be done (either overnight dexamethasone (1 mg) suppression test or a 24 h collection for urinary free cortisol). Medical Monitor (or designee) will provide guidance on the appropriate assessment based on the individual subject for subsequent test values that are also >15 nmol/L based on the subject profile.
	

Urine drug screen including amphetamines, barbiturates, cocaine metabolites, opiates, benzodiazepines and cannabinoids will be done at local laboratory using a standardized kit during screening period by Day 1. If cannot be performed during screening, test can be performed on Day 1, but must be completed before randomization procedures start.
 
Serology: HIV 1 and 2 antibodies, hepatitis B surface antigen (HBsAg), hepatitis C virus antibody, and HCV RNA (only if HCV antibody-positive)
 
Immunogenicity: Antibody to pegozafermin and NAb Endogenous FGF21
	

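### SAP 7.10.7 counts night-time salivary cortisol by a change of at least 15 nmol/L, not by the protocol's on-treatment trigger, so its summary leaves out some subjects who meet that trigger

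*SAP*

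**What the plan says.** SAP 7.10.7 gives the purpose of NSC sampling as detecting hypercortisolism during treatment. The only summary it then names is the proportion of subjects with at least "15 nmol/L change from baseline of NSC (Night-time salivary cortisol) will be summarized by treatment and placebo group".

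Protocol 8.2.5.3 uses the same figure as a level: "For on-treatment values that are >15 nmol/L AND above the screening value, a repeat NSC should be performed". If the repeat meets both conditions again, "an additional screening test for hypercortisolism will be done", either a dexamethasone suppression test (DST) or a 24-hour urinary free cortisol (UFC). Protocol Appendix 2 carries the same rule, and so does the SAP's own Appendix 3: "For on-treatment values that are >15.0 nmol/L AND above the screening value, a repeat NSC should be performed".

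Only protocol 8.2.5.3 covers an absent screening value. It keeps such subjects under follow-up ("Subjects with missing screening values will still have NSC assessments performed at the other scheduled visits") and gives them a rule: "If a screening value is not available, and on-treatment value is >15 nmol/L, a repeat NSC should be performed".

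SAP 5.1 sets baseline for measures of this kind as the value "defined as the last non-missing value collected on or before the day of first study drug dose". The schedules of activities place the only pre-dose NSC at screening. The safety endpoint in SAP 4.1.5 is the incidence and shifts of clinically significant findings, including "blood biochemistry and urinalysis, serum, salivary, and urinary cortisol as appropriate".

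**The concern.** The figure of 15 nmol/L appears to have moved from a level to a difference between protocol 8.2.5.3 and SAP 7.10.7. Neither document gives a reason for a 15 nmol/L change. The SAP is also inconsistent internally, since its Appendix 3 keeps the level.

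The stake is a prespecified safety question. A reader of the study report would probably take the 7.10.7 proportion as the answer to how often NSC was high on treatment. It would omit some subjects whom the protocol sends for a repeat sample, including some whose repeat leads on to DST or UFC. Section 7.10.7 also leaves open the direction of the change, whether it is judged at any visit or at each visit, and whether subjects without a baseline stay in the denominator.

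**Working it through.** The documents give no expected NSC rate or event count, so there is no planned figure to reproduce. The check compares the two rules directly.

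**Notation.** s is the screening NSC and x an on-treatment NSC, both in nmol/L.

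- SAP 7.10.7, read as a rise: x − s ≥ 15, that is x ≥ s + 15.
- Protocol 8.2.5.3, s available: x > 15 and x > s, that is x > max(15, s).
- Protocol 8.2.5.3, s missing: x > 15.

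**Is one rule inside the other?** SAP 7.10.1 sets laboratory values below the quantification limit to half that limit, so s > 0. Then x ≥ s + 15 implies both x > 15 and x > s. Every subject counted by 7.10.7 therefore meets the trigger. A grid check with s from 0.1 to 40 and x from 0.1 to 80 found no exception.

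**Who is missed?** Subjects with max(15, s) < x < s + 15. The gap is s wide when s ≤ 15 and 15 wide when s > 15.

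| Screening s | Trigger met above | 7.10.7 met from | Missed values of x |
|---|---|---|---|
| 2 | 15 | 17 | >15 to <17 |
| 5 | 15 | 20 | >15 to <20 |
| 10 | 15 | 25 | >15 to <25 |
| 20 | 20 | 35 | >20 to <35 |
| missing | 15 | undefined | all above 15 |

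**Example.** With s = 4, x = 18 and a repeat of 18, the subject goes on to DST or UFC under the protocol, because 18 > 15 and 18 > 4 both times. The change is 18 − 4 = 14, so 7.10.7 does not count the subject.

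**The lower limit matters.** With s = 20 and x = 18, the value lies between 15 and s + 15 = 35 but does not trigger, because 18 is below 20. Screening values above 15 are not exclusionary, so the gap must start at max(15, s), not at 15.

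**Share missed.** This depends on the NSC distribution, which the documents do not give. As an assumption only, NSC was taken as lognormal with median 2 to 8 nmol/L, log-SD 0.5, 0.8 or 1.1, screening to on-treatment correlation 0.3 or 0.6, and an on-treatment multiplier of 1, 2 or 4. Across the 70 scenarios with enough triggering subjects to evaluate, the missed share of triggering subjects ran from 17% to 97% and exceeded one half in 30.

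**Weight of one subject.** On the planned numbers in SAP Table 1, one missed subject is 1/16 = 6.3 percentage points at 15 mg QW, 1/40 = 2.5 at 44 mg Q2W, and 1/64 = 1.6 at 30 mg QW or pooled placebo (42 + 22 = 64).

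**The case against.** The best defence is that the 8.2.5.3 rule is a prompt for a repeat sample, not a case definition or a named endpoint. A change summary is also legitimate in itself: screening 20 with 20.1 on treatment meets the trigger but says little about a drug effect. This stands. It is a reason to keep the change-based table, not to leave the trigger untabulated when 7.10.7 gives hypercortisolism on treatment as its purpose.

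Other SAP output might also pick up high NSC. SAP 7.10.1 summarizes abnormal values and shifts for an unspecified selection of other laboratory tests, Appendix 3 lists NSC among the study-specific tests, and findings judged clinically relevant may appear as adverse events. NSC is not named in that selection, and the table shells are separate documents. Those shift tables use normal ranges, not the screening-dependent rule. Under SAP 6.2 a valid scheduled result is preferred, so unscheduled repeats would generally drop out of by-visit tables. The objection succeeds in confining the point to the 7.10.7 summary.

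A reader might infer that every subject randomized without an NSC result is lost. The documents do not support that. Protocol 8.2.5.3 lets subjects be randomized while a submitted sample is still pending, and that sample later supplies a baseline under SAP 5.1. Only truly missing pre-dose samples leave no change score.

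**Conclusion.** The mismatch is real, and its direction is certain for any positive screening value. The 7.10.7 proportion is a strict subset of the subjects meeting the protocol trigger. It omits those with max(15, s) < x < s + 15 and those who trigger with no pre-dose NSC.

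Three stronger conclusions are tempting and unsupported:

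- **That most triggering subjects are missed.** The documents give no NSC distribution, and under the assumed ones the share falls on either side of one half.
- **That these subjects go uncounted throughout the SAP.** The laboratory section does not say whether NSC is among its selected tests.
- **That the summary is biased toward finding no difference from placebo, or cannot show one.** The same cut applies to every arm. What is shown is undercounting and lost sensitivity, not differential bias.

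This is a descriptive safety table and does not touch the histological primary endpoints. It is still worth correcting before the tables are produced, because the count as written does not measure the question the section poses. The conclusion reads 7.10.7 as a rise from baseline and takes screening as the only pre-dose NSC.

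**What to change.** Reconcile SAP 7.10.7 with protocol 8.2.5.3 by adding, by treatment arm:

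1. the proportion of subjects with any on-treatment NSC meeting the 8.2.5.3 trigger, using the level-alone rule where screening is missing;
2. the proportion meeting it again on repeat, with unscheduled repeats included;
3. DST and UFC results, where performed and recorded.

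Keep the proportion with a change of at least 15 nmol/L as a supplementary table. State its direction, whether it is judged at any visit or at each visit, and how subjects without a baseline enter the denominator.

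The cost is a few SAP sentences and one more table shell. Scheduled NSC values are already collected. DST and UFC are conditional tests with no row of their own in the schedule of activities, so their capture on the case report form should be confirmed. The trigger-based proportion will be at least as high as the change-based one in every arm, and the report should explain why. Which clinical threshold is right is left to the protocol's authors.

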7.11. Serum concentration of pegozafermin

The serum concentration of pegozafermin over time will be listed by individual and summarized for each timepoint by treatment group. Serum concentration data will also be presented using arithmetic statistics. Individual and mean pegozafermin serum concentration vs. time plots will be produced on both a linear scale and on a semi-logarithmic scale.

For summarization of PK concentration values and data analysis, assessments that are below the lower limit of quantification (LLOQ) will be set to zero prior to summarization. For PK concentration graphs using a semi-logarithmic scale, assessments that are below the lower limit

of quantification will be set to half of LLOQ prior to graphing for illustration purposes. For PK concentration assessments that are above the upper limit of quantification (ULOQ), the record will be set to missing prior to summarization or graphing.

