4.1.4. Pharmacokinetics PK Endpoints

Trough concentration of pegozafermin.

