The listings will only present non-imputed data unless otherwise specified.

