7.10.1. Adverse Events

Subject incidence of TEAEs will be tabulated by MedDRA (Version 24.0) system organ class, MedDRA preferred term, and treatment groups. All TEAEs, all treatment-emergent related AEs, all TESAEs, and all treatment-emergent serious related AEs, the most severe Common Terminology Criteria for Adverse Events (CTCAE) grade, TEAEs leading to dose interruption, TEAEs leading to IP discontinuation, and TESAEs leading to IP discontinuation will be summarized. Subjects will be counted only once within a SOC and Preferred Term (PT), even if the subject experienced more than one TEAE within a specific SOC and PT, and PT only.

Selected TEAE analyses will be repeated in subgroups including age, sex, race, and BMI.

All AEs, SAEs, AEs leading to IP interruption or discontinuation, fatal AEs, and COVID-19 related AEs will be listed with TEAE flags included.

Clinical Laboratory Parameters

Clinical laboratory tests listed in ([Clinical Laboratory Tests](#)) will be collected during the study.

For all other assessments that are below the lower limit of quantification will be imputed to half of the lower limit of quantitation (LLOQ) for summarization; assessments that are above the upper limit of quantification will be imputed to the upper limit of quantitation (ULOQ) for summarization. For listings, records that are LLOQ or ULOQ will be listed as such together with the imputed value in separate columns.

For all hematology, biochemistry urinalysis tests, coagulation factors, lipid assessments, and selected other laboratory assessments, descriptive summaries of absolute values and change from baseline at each scheduled assessment will be produced by treatment groups, the number and percentage of subjects with abnormal laboratory values will be summarized.

Shifts (low/normal/high) from the relevant baseline tables based on the normal ranges will be constructed. The shifts will be performed from the baseline to each post-baseline visit, and to minimum and maximum post-baseline visit.

A summary of suspected liver injury cases according to drug induced liver injury (DILI) criteria will also be presented ([Table 6](#)).

Table 6: Suspected liver injury cases according to drug induced liver injury (DILI) criteria

Baseline Value of ALT/AST	Criteria to discontinue investigational product
>ULN and <2× ULN	ALT or AST >5× baseline value
>=2× ULN but <5× ULN	ALT or AST >3× baseline value
>=5× ULN	ALT or AST >2× baseline value

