			Q2W from Weeks 2 to 22		Q2W from Weeks 24 to 46								n. IP will be administered SC to the abdomen by trained and qualified study personnel, site staff at clinic visit(s), or at home by healthcare professional, or subject's caregiver for home administration. IP may also be self-administered at the subject's home.	
													o. Week 26 may be an in-clinic or a remote/home visit by healthcare professional who will administer the IP.	
PK blood collection ^p		B	B	B	B		B			B	X	X		p. PK blood samples will be collected predose. Additional blood samples for PK analysis may be collected if clinically indicated (e.g., in case of SAE). For PK sample collection instruction/procedures, refer to the relevant manual.

Assessments	Screening Period ¹	Treatment Period										FU Period	Notes:
		Main Study					Extension Study						
Study Day		1 ²											
Study Weeks	-12 to 0		4 ³	8 ⁴	12 ³	16 ⁴	24 ³	26 ⁵	30 ⁴	38 ³	48 ³	ET ^{3,6}	51 ⁷ /EOS
Visit window (days)			±2	±7	±7	±7	±7	+7	±7	±14	+14		±14
ELF panel, Pro-C3, adiponectin, FIB-4 index (derived calculation), and adipo-IR (fasting free fatty acids x fasting insulin)		B		X		X			X	X	X		Refer to Appendix 2 (Section 10.2).
Night-time salivary cortisol (NSC) ^q	X ^q			X	X			X	X	X			q. NSC sample will be collected by subject at home between 8:00pm and 12:00am before submitting the sample for processing at the specified visit. If the sample is not collected between 8:00pm and 12:00am, the test should be repeated. The screening assessment should be performed as early as possible during the screening period. Subjects should be provided with NSC collection kit at the first screening visit, when possible, to allow sample collection return at the following clinic visit. If screening value is >15 nmol/L, Medical Monitor (or designee) may request further workup should the value be of clinical concern; however, values >15 nmol/L will not be exclusionary. The screening NSC is a safety assessment, and not an I/E criteria. Refer to Section 10.2 for further requirement for Value >15 nmol/L on treatme

Assessments	Screening Period ¹	Treatment Period										FU Period	Notes:
		Main Study					Extension Study						
Study Day		1 ²											
Study Weeks	-12 to 0		4 ³	8 ⁴	12 ³	16 ⁴	24 ³	26 ⁵	30 ⁴	38 ³	48 ³	ET ^{3,6}	51 ⁷ /EOS
Visit window (days)			±2	±7	±7	±7	±7	+7	±7	±14	+14		±14

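### SAP 7.11 sets pegozafermin concentrations above the ULOQ to missing, so whenever the rule applies the mean trough for that arm and visit is biased downward

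*SAP*

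**What the plan says.** SAP 7.11 summarizes serum pegozafermin by time point and treatment group, with individual and mean concentration-time plots. It adds that "Serum concentration data will also be presented using arithmetic statistics".

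The two ends of the assay range are handled differently. Assessments "below the lower limit of quantification (LLOQ) will be set to zero prior to summarization" and so stay in the calculation. For those above the ULOQ, "the record will be set to missing prior to summarization or graphing".

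For clinical laboratory parameters (under SAP 7.10.1), "assessments that are above the upper limit of quantification will be imputed to the upper limit of quantitation (ULOQ) for summarization", and the listings show the reported result beside the imputed one.

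The data concerned are those of the secondary endpoint "Trough concentration of pegozafermin" in SAP 4.1.4, which SAP 4.2.2 repeats for the Extension Study. The schedule of activities says that "PK blood samples will be collected predose". SAP 4.1.5 also names a safety endpoint that draws on these concentrations: "Impact of the presence of ADAs on serum pegozafermin concentrations and clinical safety".

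Neither document gives the ULOQ, the share of samples expected above it, a dilution and re-assay step, or a count of records removed.

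**The concern.** A concentration reported as above the ULOQ is not unknown: it is higher than every quantified value. Setting it to missing selects records on the value being summarized, and always at the high end. At the low end, a value below the LLOQ is replaced by the smallest value that it could have. Both rules therefore pull the arithmetic mean down.

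At stake is the accuracy of the reported mean trough and its spread. Arms with higher exposure would lose the most records, so differences between arms would look smaller than they are. Groups are planned at 16, 40 and 64 subjects (SAP Table 1), so a few removed records can move a mean. Because the removed records are not counted, a reader of the summary could not see that this had happened.

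**Working it through.** The plan states no figure to reproduce. The check covers the direction first, then the size under stated assumptions.

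**Direction of the mean.** Let k of n values exceed the ULOQ, with 0 < k < n. Every removed value is larger than every retained value, so the retained mean is below the full mean. This needs no distributional assumption. If k = 0 the rule does nothing.

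**Direction of the SD.** Removing one value x lowers the sample SD only if (x − mean)² > s²(n − 1)/n. That is usual for the top of a right-skewed sample but not guaranteed. In the left-skewed set 0, 5, 8, 9, 9.5, 9.8, 10, 10, 10, 10, removing the four values of 10 lowers the mean from 8.13 to 6.88 but raises the SD from 3.25 to 3.79.

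**Size.** Assumptions not in the documents: lognormal troughs scaled to mean 1, coefficient of variation CV, share p above the ULOQ, none below the LLOQ. Let σ = √ln(1 + CV²), z = Φ⁻¹(1 − p), and ULOQ = c = exp(σz − σ²/2).

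- Mean after deletion = Φ(z − σ)/(1 − p)
- Mean after setting to the ULOQ = Φ(z − σ) + p·c

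For CV 50%, σ = √ln 1.25 = 0.4724.

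- p = 1%: z = 2.3263, c = 2.684, Φ(1.854) = 0.9681. Deleted: 0.9681/0.99 = 0.978, or −2.2%. Set to ULOQ: 0.9681 + 0.0268 = 0.995, or −0.5%.
- p = 5%: z = 1.6449, c = 1.945, Φ(1.172) = 0.8795. Deleted: 0.8795/0.95 = 0.926, or −7.4%. Set to ULOQ: 0.8795 + 0.0973 = 0.977, or −2.3%.

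Over a wider range:

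| Assumed CV | Share above ULOQ | Mean, deleted | Mean, set to ULOQ | SD, deleted | SD, set to ULOQ |
|---|---|---|---|---|---|
| any | 0% | 0 | 0 | 0 | 0 |
| 30% | 1% | −1.1% | −0.2% | −6.9% | −2.6% |
| 30% | 5% | −4.0% | −1.1% | −18% | −9.6% |
| 50% | 1% | −2.2% | −0.5% | −10% | −4.6% |
| 50% | 5% | −7.4% | −2.3% | −25% | −14.5% |
| 50% | 10% | −12.1% | −4.5% | −35% | −23% |
| 80% | 5% | −13.0% | −4.9% | −35% | −23% |

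In simulations with 5% of values set to zero as below the LLOQ, the mean and SD still fell in every scenario tested.

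**Contrast between arms.** Suppose two arms share one ULOQ, with a true mean ratio of 2 and CV 50% in each (assumptions). If 5% of the higher arm exceeds the ULOQ, its retained mean is 2 × 0.926 = 1.85, while the lower arm has only about 0.1% above and barely changes. The observed ratio is about 1.86, against 1.95 with values set to the ULOQ.

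**The case against.** The strongest answer is that the rule may never operate. Samples are taken predose, and Protocol 4.3 puts group tmax at 48 to 72 hours after dosing with accumulation ratios of only 1.0 to 1.4. Troughs therefore sit in the lower part of each profile. Over-range samples are often diluted and re-assayed, and the laboratory's procedures may already provide for this, but they are not in the documents. This stands. It makes the size unknown and possibly zero, but it does not make the rule right when it applies.

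Second, the consequences are limited. The plan for these data is listings, descriptive summaries and plots, with no hypothesis test. SAP 7.1 adds that "The listings will only present non-imputed data unless otherwise specified", so the original results remain visible. Any population PK modelling may have its own analysis plan. This also stands.

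Third, the laboratory rule is expressly for other assessments, so the SAP does not contradict itself. That is correct. The laboratory rule matters here only as a less biased convention already in the same document, and it too leaves some downward bias.

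A reader might also infer that dose selection or the antibody analysis would be distorted. The documents do not support either. The stated purpose of trough sampling is to characterize the PK profile. Protocol 4.2 ties dose selection to the efficacy data, in particular the histology. For antibodies, Protocol 9.4.2 says only that the effect on concentrations may be evaluated, and SAP 7.10.6 plans no such analysis.

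**Conclusion.** The point holds, as a minor one. Whenever some but not all records at a time point exceed the ULOQ, SAP 7.11 gives a mean trough for that arm that is too low, and the higher-exposure arms would be affected most. The fall in the mean is certain in that case. The fall in the SD is what right-skewed data usually show, so it should not be stated as a necessity.

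The size cannot be derived from the documents. It runs from zero upward: at an assumed CV of 50%, about 2% of the mean with 1% of values above the ULOQ and about 7% with 5%. The primary histology results, power and type I error are untouched.

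**What to change.** Replace the ULOQ sentence in SAP 7.11 with a rule along these lines:

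- Where a valid diluted re-assay result is available, use it.
- Otherwise, set the value to the ULOQ for summaries and graphs, as the SAP already does for laboratory tests, and flag it.
- In addition, report the number of such records by arm and time point. SAP 7.10.1 does not require this count for laboratory tests, so it is a new item.

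The cost is a short amendment to SAP 7.11 and one extra table row, with no change to trial conduct. A small downward bias remains wherever values are set to the ULOQ, and the reported count lets the reader judge whether it matters.
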